Written consent will be obtained from subjects who are eligible participants based upon their medical condition (as determined by their physician). The consent process will take place during an office visit at which time the investigator has determined subject's voluntary participation has been upheld. Subjects will be informed about the study and the intended purpose. They will be given the opportunity to ask questions and receive thorough explanations. They will be made aware of the possible risks and anticipated benefits. They will also be informed of alternative procedures. Subjects will then be given another opportunity to ask questions and agree or disagree to consent.

Subject Capacity

All subjects enrolled in this study will have capacity to provide informed consent.

Debriefing Procedures

No information will be withheld from the subject. Patients will be told if they received the calibrated or non-calibrated device after completing the study.

Consent Forms

Informed consent will be obtained from all subjects and documented with a signed, written consent form using the NYU SoM's English standard consent form.

Documentation of Consent

In addition to following the consent process, it is understood by the study staff that retrieving informed consent is an ongoing process that continues after the actual informed consent has been signed. There is

CONFIDENTIAL

This material is the property of the NYU School of Medicine and Langone Medical Center. Do not disclose or use except as authorized in writing by the study sponsor

a "Documentation of Consent" checklist that will be used as additional documentation. This form will serve as secondary proof that the informed consent process has been executed.

Costs to the Subject

Subjects will not incur any additional financial costs as a participant in this study beyond those normally associated with this type of condition. All procedures (physical exam and radiographic imaging) performed in this study will be billed to the patient/patient's insurance provider, hospital insurance or third party payer as per standard of care. The study device (AposTherapy®) and the study questionnaires are being provided by the sponsor free of charge.

Payment for Participation

No payments/reimbursements will be provided to subjects for their participation in this study.

CONFIDENTIAL

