The Apos Device. (a) Biomechanical device comprising two individually calibrated elements and a foot-worn platform. The elements are attached to a platform under the hindfoot and forefoot regions. (b) The biomechanical elements are available in different degrees of convexity and resilience. (c) The specially designed sole of the platform includes two mounting rails and a positioning matrix to enable flexible positioning of each biomechanical element. [Elbaz, 2014].

Figure 2. The sham device

CONFIDENTIAL

This material is the property of the NYU School of Medicine and Langone Medical Center. Do not disclose or use except as authorized in writing by the study sponsor

Objectives and Hypothesis of Study

1. The primary objective is to evaluate the efficacy of AposTherapy® at 6 months, with the primary efficacy assessment based on improvement in knee pain score and improvement in function in patients with knee OA. The hypothesis is that patients fitted with the calibrated AposTherapy® device will demonstrate an improvement in knee pain intensity and improvement in function compared to patients who are fitted with a sham-placebo Apos device.
2. After completion of 6 months of therapy, patients will be un-blinded to their group allocation and the second phase of the study will commence, including the following aims:
 - a. To evaluate the long-term (12 months) effect of AposTherapy® on the level of pain and the level of function of patients with knee OA. We hypothesize that patients will maintain the diminished levels of pain and improved function.
 - b. To evaluate the changes in the level of pain and the level of function of patients that were originally allocated to the control group and will now cross-over and commence AposTherapy® treatment for 6 months. We hypothesize that patient will report an improvement in the level of pain and improvement in function following 6 months of treatment.

Primary Efficacy Endpoints

- Phase I:
 - Improvement in knee pain score and improvement in function, as measured by change from baseline Western Ontario and McMaster University (WOMAC) score to 6 months post treatment.
- Phase II:
 - Long-term effect (12 months) of AposTherapy on pain and function, as measures by WOMAC, of patients with knee OA
 - Improvement in knee pain and knee function, as measured by WOMAC, of patients with knee OA that were allocated to the sham control group and have crossed-over to the active group, receiving AposTherapy for 6 months.

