Secondary Efficacy Endpoints

- Phase I:
 - Improvement in WOMAC scores between all study time points – pre-treatment and following 3 months and 6 months post-treatment;
 - Improvement in Visual Analog Score (VAS) score between all study time points;
 - Improvement in Short-Form 36 (SF-36) score between all study time points;
 - Reduction in usage of pain killers or NSAIDS
- Phase II:
 - Original Active group - Improvement in knee pain and knee function scores, as measured by change from baseline WOMAC score to 12 months post treatment;
 - Original Active group - Improvement in VAS score between baseline and 12 months post treatment;
 - Original Active group - Improvement in SF-36 score between baseline and 12 months post treatment;
 - Original Active group - Reduction in usage of pain killers or NSAIDS
 - Cross-over group - Improvement in WOMAC scores between all study time points – pre-treatment and following, 3 months and 6 months post-treatment;
 - Cross-over group - Improvement in Visual Analog Score (VAS) score between all study time points;
 - Cross-over group - Improvement in Short-Form 36 (SF-36) score between all study time points
 - Cross-over group - Reduction in usage of pain killers or NSAIDS

CONFIDENTIAL

This material is the property of the NYU School of Medicine and Langone Medical Center. Do not disclose or use except as authorized in writing by the study sponsor

Outcome Measure Evaluation Criteria

Western Ontario and Mac Master University (WOMAC) – the WOMAC is a self-administered osteoarthritis outcomes instrument designed to assess lower extremity pain and function in osteoarthritis of the knee or hip. The minimal clinically important difference (MCID) proportion is a 16.0% reduction in WOMAC [Hmamouch, 2014].

Visual Analog Score (VAS) Scale - the VAS is a validated pain scale that asks subjects to rate the amount of pain they are currently experiencing on a line up to 100mm (no pain is equal to 0mm and the worst imaginable pain is equal to 100mm). An improvement of 20 points from the baseline score is considered a statistically significant improvement at that visit [Gallagher, 2001].

Short-Form (36) Health Survey – the SF-36 is a patient reported survey of health that is designed to measure health status. The survey consists of eight (8) sections, where the lower the score the more disability and the higher the score the less disability [Maruish, 2009].

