- Patients who have had a joint replacement or other major surgery to the knee, hip or ankle (ipsilateral or contralateral side).
- Patients suffering from neuropathic arthropathy.
- Patients with an increased tendency to fall.
- Patients exhibiting a lack of physical or mental ability to perform or comply with the study procedure.
- Patients with a history of pathological osteoporotic fracture.
- Patients suffering from symptomatic degenerative arthritis in lower limb joints other than the knees.
- Patients with referred pain in the knees from primary back or hip joint pain.
- Patients with neurological deficits to the lower extremity (ex. foot drop)
- Patients whose shoe size is less than US 4 and greater than US 12
- Patients who have had arthroscopy within 6 months of the study
- Patients with inflammatory arthropathy
- Patients with any central nerve system disease/neurological problem (i.e. Parkinson's, post CVA (stroke), etc.).

Vulnerable Subjects

We do not intend to enroll vulnerable subjects.

Subject Withdrawal

Patients are free to withdraw at any time from the study. While participating in the study, patients should avoid any other treatment modality apart from rescue pain medication (Acetaminophen/Paracetamol) as long as it is possible. If patients require injection therapy or surgery on the study knee(s) during the course of the study, the patient will be withdrawn from further data collection.

III. METHODS AND PROCEDURES

Sample Size Analysis

Assuming normality on the data, we calculated the statistical power for various detectable effect sizes listed in Table X using PASS 2011 software (http://www.ncss.com/download_PASS11.html). The analysis of power is performed conservatively by assuming the largest variability in pain scores observed in the preliminary data (e.g., reduction of pain scores of 3.0 in active group and 0 of control group with a pooled standard deviation of 3.60 corresponds to an effect size of 0.8. After accounting for a 10% loss to follow-up we would expect to enroll 60 patients in each group for a total of 120 patients. With 120 samples (60 each), the two-sided t-test will have 80% power at the 0.05 significance level to detect differences of pain score of 0.8 SD units between control and case [Bar-Ziv, 2013].

Methods and Procedures

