Patients that were allocated to the control group will receive the AposTherapy® device and treatment. The device, with calibrated elements, will be individually calibrated to the patients according to his/her clinical condition. During their daily routine, patients will be asked to wear their custom-worn device for approximately 2 hours per day, throughout the study duration, starting with less than an hour of walking around the house and gradually increasing wearing time to outdoor walking. Patients that crossed from the control group to the active group will be assessed after 3 months and 6 months from commencement of phase II. The results of the 6 months will serve as their new baseline results for phase II of the study. Patients will be asked to come to follow-up visits at the treatment center (located at [name]) at the following time points: 27 weeks from original baseline, 36 weeks from original baseline, 42 weeks from original baseline, and 52 weeks from original baseline. During these visits the biomechanical device will be adapted according to the clinical needs of the patient.

CONFIDENTIAL

This material is the property of the NYU School of Medicine and Langone Medical Center. Do not disclose or use except as authorized in writing by the study sponsor

Study schedule:

Study Periods	Screening	Treatment, Intervention Period									
		1	2	3	4	5	6	7	8	9	10
Time (week)	-2	0	3	7	12	18	24 – final assessment for phase I, un-blinding patients, cross-over design and commence of phase II	27 – only for patients that crossed-over from the control group to the intervention group	36	42	52
Patient Information and Informed Consent (at NYULMC)	X										
Demographics (at NYULMC)	X										
Medical History (at NYULMC)	X										
In- /Exclusion Criteria (at NYULMC)	X										
Full Research Assessment (Physician) (at NYULMC)	X				X		X		X		X
Radiography (at NYULMC)	X										
Randomization (at NYULMC)	X										
Concomitant Therapy (at NYULMC)	X				X		X		X		X
Primary Variables (at NYULMC)	X				X		X		X		X
Secondary Variables (at NYULMC)	X				X		X		X		X
Adverse Events (at NYULMC)					X		X		X		X
Administer Medical Device (at Apos Center)		X					X – for patients who crossed-over from control to active				
Adjustment Medical Device (at Apos Center)			X	X	X	X	X – active group	X	X	X	X

CONFIDENTIAL

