This material is the property of the NYU School of Medicine and Langone Medical Center. Do not disclose or use except as authorized in writing by the study sponsor

Data Analysis

Phase I:

- Primary outcome measures will include comparing scores at baseline and the following study time points (baseline, 3 months and 6 months) obtained from the WOMAC. The WOMAC is a validated outcomes assessment used to measure patients' opinion about their knee and associated problems.
- Secondary outcome measures will include comparisons of all measured variables between baseline and all time points including VAS score, SF-36 score, improvement and maintenance in knee function using physical examination findings (these include, but are not limited to: Pain, Knee Effusion, Ligament Stability, Stability, Strength, Range of Motion, Sensation, Posture/alignment); and monitoring usage of rescue medications or NSAIDs. All data will be obtained from the completed case report forms that are being utilized for this study.

Phase II:

- Original active group – evaluating the changes in pain, function, quality of life and usage of rescue medications or NSAIDs following 12 months of therapy.
- Cross-over group – comparing scores at baseline and the following study time points (baseline, 3 months and 6 months) obtained from the WOMAC, SF-36, knee function and usage of rescue medications or NSAIDs.

DATA SAFETY MONITORING PLAN (DSMP)

I. Study Monitoring

The principal investigator, [name], will be the data safety monitor for this project. After a three (3) months follow-up period, [name] will review the data for SAE's, protocol deviations and other issues. If it is determined that certain events occur above an expected rate (i.e. increased knee pain), then enrollment will be stopped.

II. Types of Data

Under this DSMP, the following data/events will be captured and documented:

- Duration of AposTherapy® use;
- Monitoring of patient falls;
- Patient Outcomes Assessments;
- Reportable and/or adverse events
- Protocol Deviations

III. Responsibilities and roles for gathering, evaluating and monitoring the data:

Principal Investigator

After a three (3) months follow-up period, the PI will meet with any co-investigators and the Research Coordinator to discuss the current findings and analysis. During these meetings, the PI will also be responsible for verifying data accuracy, and compliance with the study protocol.

Research Coordinator

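### Hypothesis 2a is about holding the month-6 benefit to month 12, but the only explicit 12-month contrasts for the original active group are against baseline, and no month-6-to-12 contrast is given

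*Combined protocol and SAP*

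**What the plan says.** All references are to the combined protocol and SAP.

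- **Objectives and Hypothesis of Study, item 2a.** After unblinding at 6 months, the long-term aim for patients on the device carries this hypothesis: "We hypothesize that patients will maintain the diminished levels of pain and improved function".
- **Primary Efficacy Endpoints, Phase II.** The matching endpoint is "Long-term effect (12 months) of AposTherapy on pain and function, as measures by WOMAC, of patients with knee OA". It names no reference time, test or margin.
- **Secondary Efficacy Endpoints, Phase II, original active group.** WOMAC pain and function are to be assessed "as measured by change from baseline WOMAC score to 12 months post treatment". VAS is worded the same way: "Original Active group - Improvement in VAS score between baseline and 12 months post treatment". SF-36 also runs from baseline to 12 months. The analgesic-use endpoint names no reference time.
- **Data Analysis, Phase II, original active group.** The whole description is "evaluating the changes in pain, function, quality of life and usage of rescue medications or NSAIDs following 12 months of therapy". Again there is no comparator, test or decision rule.
- **Phase II design text.** Month 6 is made a reference point, but only in the paragraph on control patients who cross over: "The results of the 6 months will serve as their new baseline results for phase II of the study".

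**The concern.** To maintain a level is to stay at it once it has been reached. Item 2a follows the month-6 unblinding and speaks of improvement already achieved, so the quantity it concerns is the change from month 6 to month 12. A difference between month 12 and baseline answers another question: whether any net improvement remains. That difference can be clearly above zero while much of the month-6 benefit has gone.

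At stake is the durability statement that Phase II is meant to support. If the analysis follows the contrasts that are written down, a significant improvement over baseline at 12 months would be the natural result to cite under 2a, although it does not test 2a. There is also no randomized comparison to fall back on, because after month 6 "Patients that were allocated to the control group will receive the AposTherapy® device and treatment".

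**Working it through.** **1. The plan's own figure.** The plan states no power or precision for the 12-month aim. Its 80% power statement in Sample Size Analysis belongs to the 6-month between-group comparison and is not used here.

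**2. Hypothesis and contrasts side by side (original active group).**

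| Element | Quantity named | Reference time |
|---|---|---|
| Hypothesis 2a | Pain and function maintained | Month 6, by meaning |
| Phase II primary endpoint | WOMAC pain and function, 12 months | None named |
| Secondary: WOMAC, VAS, SF-36 | Change to 12 months | Baseline |
| Secondary: analgesic use | Reduction | None named |
| Data Analysis, Phase II | Changes after 12 months of therapy | None named |

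No row gives month 12 against month 6.

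**3. How little a baseline contrast says about maintenance (illustration).**

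Inputs from Sample Size Analysis:
- "reduction of pain scores of 3.0 in active group and 0 of control group with a pooled standard deviation of 3.60"
- two-sided 0.05
- 60 per arm with 10% loss, so 60 × 0.9 = 54 evaluable.

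Assumption: the documents give no within-patient SD or correlation. Taking 3.60 as the SD of a single score, the SD of a paired change is 3.6 × √(2(1 − ρ)):
- ρ = 0.5: 3.60
- ρ = 0.7: 2.79
- ρ = 0.3: 4.26

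One-sample t-test of month 12 minus baseline, n = 54, critical t (53 df) = 2.006:
- Standard error = 3.6/√54 = 0.490.
- Smallest significant observed mean change = 2.006 × 0.490 = 0.98 points, or 0.98/3.0 = 33% of the planned gain (25% to 39% over the SD range).
- Half the gain lost, 1.5 left: noncentrality 1.5/0.490 = 3.06, probability of significance 85% (72% to 97%).
- Two thirds lost, 1.0 left: noncentrality 1.0/0.490 = 2.04, probability of significance 52% (40% to 73%).

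A simulation of 20,000 trials (n = 54, score SD 3.6, correlation 0.5 between all visits) with two thirds of the gain lost gave significance against baseline in 52%. In 50% of all trials, month 12 was both significantly better than baseline and significantly worse than month 6.

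**4. What the month-6-to-12 contrast could deliver.** Maintenance is concluded if the two-sided 95% CI for worsening lies below a margin M. With no true loss, power follows from the same noncentral t, with M in place of the mean:

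| Margin M | Power, 54 evaluable | Evaluable n for 80% power |
|---|---|---|
| 1.5 points (half of 3.0) | 85% (72% to 97%) | (3.6 × 2.80/1.5)² → 46 (28 to 64) |
| 1.0 point | 52% (40% to 73%) | (3.6 × 2.80/1.0)² → 102 (62 to 143) |

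The n column uses the normal approximation, with 1.960 + 0.842 = 2.80. In the same simulation with two thirds lost, the 1.5-point rule passed in about 0.1% of trials and the 1.0-point rule in none.

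The 85% and 52% recur in steps 3 and 4 because 1.5 and 1.0 serve once as remaining benefit and once as margin.

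**The case against.** **The plan does not say that a significant baseline change means maintenance.** This is correct. A reader might infer that the plan would declare 2a confirmed on a significant month-12-versus-baseline result. No Phase II test, alpha or success rule is written, and the t-test above is supplied for illustration. Wrong confirmation is something the plan leaves open, not something it prescribes.

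**Not every Phase II endpoint is measured from baseline.** This is also correct. The baseline reference is explicit only for three secondary endpoints. For the primary endpoint and the Data Analysis text, the defect is an unnamed contrast rather than a wrong one. The gap for 2a remains either way.

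**Fading would be visible.** The baseline-to-6-month WOMAC change is the Phase I primary endpoint and the baseline-to-12-month change is a secondary one, so the two means can be set beside each other. That is fair, but two means give neither a paired interval nor a standard for how much loss is acceptable.

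**Change from baseline suits the stated aim of evaluating a long-term effect.** It does as a description, and it should stay. It does not address the hypothesis attached to that aim.

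**The percentages look firmer than they are.** The 3.60 is a pooled pain-score SD for a two-group test, neither a WOMAC figure nor a within-patient change SD. The 10% loss has no time point, so 54 at month 12 is an assumption. The percentages show the mechanism and do not predict this trial's WOMAC results.

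**Conclusion.** The mismatch stands on the text alone: hypothesis 2a concerns months 6 to 12, the only explicit 12-month contrasts for the original active group are against baseline, and no month-6-to-12 contrast or margin is specified. Confidence in that is high.

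The size is illustrative. Under the assumptions above, a baseline test would remain significant more often than not with half the planned gain gone, and about as often as not with two thirds gone. This rests on the pain-score planning figures, visit correlations of 0.3 to 0.7 and 54 evaluable patients.

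The randomized 6-month comparison is unaffected. The point should be settled before the Phase II data are analysed, because a margin chosen after seeing them would carry little weight.

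**What to change.** 1. For the original active group, name the within-patient change in WOMAC pain and in WOMAC function from month 6 to month 12, each with a 95% CI, as the analysis of hypothesis 2a.
2. Keep the baseline-to-12-month change as a description of the long-term effect.
3. Claim maintenance only if the CI excludes worsening beyond a margin that is justified and fixed beforehand. The 16% WOMAC figure under Outcome Measure Evaluation Criteria is a clinically important difference for improvement. Using it as a tolerance for worsening would need its own justification and a statement of which score it is a percentage of.
4. State how patients who leave data collection under Subject Withdrawal enter this contrast. Those who need injection or surgery on the study knee are removed, so an analysis of completers alone could look too favourable.
5. Make the Phase II primary endpoint and the Data Analysis text name the same reference time.

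**Cost.** No new visit or measurement is needed: the schedule already collects WOMAC at weeks 24 and 52. Maintenance becomes harder to claim. With no true loss and 54 evaluable, power is about 85% at a 1.5-point margin but only about 52% at 1.0 point, so a strict margin may be out of reach at this sample size. Phase II is open-label and has no concurrent control, so the contrast describes durability and cannot attribute it to the device. The plan should say so.

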At each follow-up visit, subjects will be asked on their use of any rescue medications or therapy for their knee pain. Rescue medications or therapy will include, but are not limited to, NSAIDs, physical therapy and surgical interventions. While participating in the study, subjects should refrain from taking corticosteroid and/or hyaluronic acid injections. Subjects will also be asked about their compliance with the device (ex. how long and how often the device was worn?). Research personnel will collect and record such data and note when the subject had the intervention.

Additionally, at each follow-up visit, subjects will be asked to report any changes in their knee symptoms. This change in symptoms can include, but are not limited to, pain, swelling, redness, or any overall changes in their health since the screening/baseline visit. Research personnel will collect and record such data and note when these changes occurred.

II. CHARACTERISTICS OF THE RESEARCH POPULATION

Number of Subjects

A total of one-hundred and twenty (120) patients will be enrolled in this study (60 patients assigned to each group).

Gender of Subjects

Men and women will be included in this study.

Age of Subjects

Subjects will be at least 45 years of age and no older than 75 years of age

Racial and Ethnic Origin

There are no enrollment restrictions based on race or ethnic origin.

Inclusion Criteria

- Males and females between the ages of 40-75;
- Patients suffering from symptomatic unilateral or bilateral knee OA at the medial compartment for at least six months;
- Fulfilling the ACR clinical criteria;
- Having radiographically assessed OA of the knee with a Kellgren-Lawrence grade more than or equal to grade 2; and,
- Having VAS-Pain ≥ 3 , on a scale between 0-10.
- Patients who have a shoe size between US 4 and US 12

Exclusion Criteria

- Patients suffering from acute septic arthritis.
- Patients who received a corticosteroid injection within 3 months of the study.

CONFIDENTIAL

This material is the property of the NYU School of Medicine and Langone Medical Center. Do not disclose or use except as authorized in writing by the study sponsor

- Patients who received hyaluronic acid (HA) injections within 6 months of the study
- Patients suffering from avascular necrosis of the knee.
- Patients with a history of knee buckling or recent knee injury.

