During the baseline visit, the Apostherapy® team will meet with the patient to set them up with their device. Utilizing state-of-the-art technology, an in-depth analysis consisting of step length; load distribution on each leg; walking velocity; and gait symmetry, will be obtained. A personally-calibrated device will not be used for patients randomized to this group. The patient will receive a sham-placebo foot-worn biomechanical device. During their daily routine, patients will be asked to wear their custom-worn device for approximately 2 hours per day, up until the 6 month follow-up visit, starting with less than an hour of walking around the house and gradually increasing wearing time to outdoor walking. Patients will be asked to come to follow-up visits at the treatment center (located at [name]) at the following time points: 3 -4 weeks, 7 weeks, 12 weeks, 18 weeks, 24 weeks, 27 weeks, 36 weeks, 42 weeks and 52 weeks. During these visits the biomechanical device will be adapted according to the clinical needs of the patient (this will have no actual effect on the biomechanical device, since there are no biomechanical element in the sham device).

Phase I Study Visits

Patients will be followed for 6 months after enrollment. Patients will be seen for a screening/baseline visit and will then return to NYULMC (the physician's office) for a follow-up visit at, 3 months and 6 months from initial visit.

VISIT 1/2 - Screening/Baseline visit (the screening/baseline assessments may be completed in more than one session):

The following procedures will be conducted at the physician's office located at NYULMC Center for Musculoskeletal Care, [name]:

- Sign Informed Consent Document;
- Review Inclusion/Exclusion Criteria;
- Randomize patient to one of two study arms;
- Review and document demographics, medical/surgical/concomitant medication history (complete data collection form);
- Physical Knee Evaluation (will include the following, but not limited to):
 - Pain: Note location and activities that increase and decrease symptoms, joint line tenderness, etc.
 - Knee Effusion: Presence or absence

CONFIDENTIAL

This material is the property of the NYU School of Medicine and Langone Medical Center. Do not disclose or use except as authorized in writing by the study sponsor

- Ligament Stability: Anterior drawer test, posterior drawer test, lachman test, pivot shift, valgus/varus stress test.

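### The rule on NSAIDs is inconsistent, and the original active group's 12-month fall in painkiller or NSAID use cannot be credited to the device under either reading

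*Combined protocol and SAP*

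**What the plan says.** **Conduct and rescue.** Subject Withdrawal advises that "patients should avoid any other treatment modality apart from rescue pain medication (Acetaminophen/Paracetamol) as long as it is possible". Acetaminophen is the only drug it names as exempt. It continues: "If patients require injection therapy or surgery on the study knee(s) during the course of the study, the patient will be withdrawn". Such withdrawal means that no more data are collected.

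Outcome Measure Evaluation Criteria, in its paragraph on what to ask at follow-up visits, says: "Rescue medications or therapy will include, but are not limited to, NSAIDs, physical therapy and surgical interventions". The only restraint stated there is that "subjects should refrain from taking corticosteroid and/or hyaluronic acid injections".

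**Endpoint.** Secondary Efficacy Endpoints, Phase II, lists "Original Active group - Reduction in usage of pain killers or NSAIDS". Data Analysis, Phase II, describes the analysis of the original active group as "evaluating the changes in pain, function, quality of life and usage of rescue medications or NSAIDs following 12 months of therapy". No comparator or test is named.

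**Phase I.** A reduction in painkiller or NSAID use is also a Phase I secondary endpoint. The Data Analysis sentence on Phase I secondary measures speaks of comparisons between baseline and all time points and ends "and monitoring usage of rescue medications or NSAIDs". It does not say whether medication use is compared between arms.

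**Data.** Concomitant medication is recorded at screening/baseline and reviewed at 12, 24 and 52 weeks (also at 36 weeks for cross-over patients). No NSAID washout or stable-dose rule is stated.

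**The concern.** An endpoint that counts less medication as success needs a clear rule on what patients may take. Here one section discourages everything except acetaminophen and another treats NSAIDs as rescue. If patients record their NSAID use at baseline and are then advised to avoid NSAIDs, use can fall with no help from the device, in the direction that the plan lists as efficacy.

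The original active group is the most exposed. Its change runs from before the advice to 12 months, and by then no group remains on sham. The stake is a secondary efficacy statement that a reader might take as evidence that the device spares NSAIDs. No primary result is involved.

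**Working it through.** **1. The two sections side by side.**

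| Treatment | Outcome Measure Evaluation Criteria | Subject Withdrawal |
|---|---|---|
| Acetaminophen | not named | named as permitted rescue |
| NSAIDs | rescue | not exempt, so to be avoided where possible |
| Physical therapy | rescue | not exempt, so to be avoided where possible |
| Surgery | rescue | withdrawal, if on the study knee |
| Injections | refrain (corticosteroid, hyaluronic acid) | withdrawal, if in the study knee |

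Data Analysis adds a third usage by naming NSAIDs alongside rescue medications, as if they were separate. Nothing in the documents says which wording governs.

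**2. What the 12-month change contains.** After 6 months both groups are unblinded and the sham group receives the device. The original active group's change is therefore a sum that cannot be split:

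observed change = device effect + time trend, regression to the mean and expectation + effect of the advice on NSAIDs

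The second term is present under either rule. The third is present only if the Subject Withdrawal advice governs.

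**3. Which comparisons the advice can distort.**
- *Original active group, baseline to 12 months:* exposed, because baseline precedes the advice.
- *Phase I, between arms:* not biased in this way, because the advice applies to both arms. It may shrink a true difference.
- *Phase I, within an arm:* exposed, if that is what is meant.
- *Cross-over group, 6 to 12 months:* also uncontrolled, but its new baseline falls after the advice was already in force.

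**4. Can a size be given?** Let p be the share using NSAIDs at baseline, s the share of users who stop because of the advice, t the share of non-users who start, and q the share of stoppers who take acetaminophen. With no device effect:

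- net fall in NSAID use = p·s − (1 − p)·t
- part of the fall due to the advice that survives on a combined measure = p·s·(1 − q)

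None of p, s, t or q is in the documents. Assume p = 30–60%, s = 10–50% and t = 5–10%:
- low end: 0.30 × 0.10 − 0.70 × 0.10 = 0.03 − 0.07 = −0.04, a rise of 4 percentage points
- high end: 0.60 × 0.50 − 0.40 × 0.05 = 0.30 − 0.02 = 0.28, a fall of 28 points

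On the combined measure, the contribution of the advice runs from 0 (q = 1, everyone substitutes) to 0.60 × 0.50 = 30 points (q = 0). Even the sign of the net change depends on the assumptions.

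The chance of a significant fall in NSAID use is no more informative. With 60 × 0.90 = 54 patients, the same assumed rates and an exact McNemar test (the plan names none), it ranges from 0.02% to 98%.

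**The case against.** **The two sections can be reconciled.** The NSAID sentence sits in a paragraph about what to ask and record at visits. Its list includes surgery, which on the study knee leads to withdrawal, so being listed cannot simply mean being allowed. On this reading patients avoid other treatment where possible and staff record it when used. This is a fair reading, and it rules out calling the text a flat contradiction or an NSAID ban: the advice is softened and never names NSAIDs. It does not settle the matter. It leaves Subject Withdrawal as the only rule on conduct, and that rule discourages NSAIDs, while the other section still calls them rescue.

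**The attribution problem is not caused by the NSAID rule.** This stands. A reader might infer that the 12-month change would be sound evidence if NSAIDs were freely permitted. The documents do not support that: the change would still be open-label and uncontrolled. The advice only adds a further cause.

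**The written endpoint is wider than NSAIDs.** This also stands. Painkillers include acetaminophen, so a patient who swaps one for the other need not show a reduction. The argument about the advice reaches the NSAID part only.

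**Staff at a single center will give consistent advice.** The principal investigator is responsible for communicating study methods, so uneven instruction is only a possibility. The point does not depend on it.

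**Conclusion.** The concern holds as a minor point. The rule of conduct for NSAIDs and physical therapy is inconsistent. The original active group's 12-month change in painkiller or NSAID use cannot be attributed to the device under either reading. If Subject Withdrawal governs, the protocol's advice is an added non-device cause of a fall in the NSAID part, possibly offset by acetaminophen on a combined measure.

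The size is unknown. A reader might infer a high false-positive rate, but the documents give no usage, stopping or starting rates and no test, so no particular rate can be supported. Nor should a reader infer that the randomized Phase I comparison between arms is biased by the advice. One secondary endpoint is affected and no primary result.

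**What to change.** 1. State one rule in both Outcome Measure Evaluation Criteria and Subject Withdrawal. NSAIDs may be permitted or discouraged; either choice will do if it applies equally to both arms. Record all use. Handle study-knee injection or surgery by the existing withdrawal rule.
2. Define the Phase I medication endpoint as a between-arm comparison at 3 and 6 months, adjusted for recorded baseline use, with NSAIDs and acetaminophen reported separately.
3. Report the original active group's 12-month medication change descriptively, not as efficacy.

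The cost is small. Medication is already recorded at baseline and reviewed at the 12-, 24- and 52-week research visits, so no visit is added. What is given up is a Phase II efficacy claim on medication use that the design cannot support.
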